#### **6.1.2.1. Client Sample Recruitment**

Representative clients will be recruited from amongst employees of the study sponsor, Erchonia Corporation, who are not involved with the operation of the LunulaLaser OTC.

#### **6.1.2.2. Client Sample Compensation**

Representative clients will not receive any compensation for participation in this Human Factors Validation study.

### **6.2. DEVICE USE ENVIRONMENTS**

The Erchonia LunulaLaser™ OTC device use environments are the following non-clinical indoor environments:

1. Nail Salons
2. Beauty Salons and Spas
3. Fitness and Wellness Centers
4. Comparable facilities

The Erchonia LunulaLaser™ OTC Installation and Proper Use Reference Guide contains specific and comprehensive instructions on overall safe and effective use of the device across all intended device use environments, specifically as follows:

*Safety Information:* The *Safety Information* section contained on pages 4 through 6 of the Installation and Proper Use Reference Guide contains specific instructions for device environment restrictions and safety factors, as follows:

- PRECAUTION (page 5): **DO NOT** place/operate this device in close proximity (6 inches) to other devices that emit frequency.
- PRECAUTION (page 6): Avoid contact with flammable anesthetic with air or with oxygen or nitrous oxide.
- PRECAUTION (page 6): This device should be operated in temperatures between 59° to 85° F (15° to 29° C), ... with relative humidity less than 75%
- PRECAUTION (page 6): **Do not** position equipment so that in an emergency it is difficult to disconnect power cord from electric supply.

Relevant characteristics of the intended device use environments that were considered and accommodated during the medical device development and design process to mitigate potential conditions and factors that could affect safe and effective use of the Erchonia LunulaLaser™ OTC, are the following:

Device User Environment Characteristic	Mitigation of Consideration
Proximity to water, liquids and other foreign materials that may enter the device potentially resulting in damage to the device, user and/or treatment recipient.	 WARNING in Installation and Proper Use Reference Guide that states: DO NOT permit any foreign materials or liquids to enter the device. Take care to prevent any foreign materials including, but not limited to, inflammables, water, and metallic objects from

	
entering the device. These may cause device damage, malfunction, electrical shock, fire, or personal injury. To achieve the specified level of protection against spilled or splashed liquids, unplug the device from the power supply and thoroughly dry all exposed surfaces of this device and allow to dry thoroughly prior to operation.
 

•  WARNING: Beware of electrocution. Do not submerge any part of the device in water. This could damage the device or cause an electric shock that may lead to serious injury or death. Damage resulting from this condition is not covered under the warranty.

Proximity to other devices that emit frequency that may interfere with the accurate operation of LunulaLaser OTC.	
 PRECAUTION in Installation and Proper Use Reference Guide that states: DO NOT place/operate this device in close proximity (6 inches) to other devices that emit frequency. If this device causes interference to other devices, which can be determined by turning the device off and on, you are encouraged to try to correct the interference by one of the following measures:
 

➢ Reorient or relocate the receiving device.

➢ Increase the separation between the equipment.

➢ Connect the equipment into an outlet on a circuit different from that to which the other device(s) are connected.

### 6.3. DEVICE USER INTERFACE

The device user interface is defined as all points of interaction between the user and the device, including all elements of the device with which the user interacts (i.e., those parts of the device that users see, hear, touch). This includes all sources of information transmitted by the device (including packaging, labeling), training and all physical controls and display elements (including alarms and the logic of operation of each device component and of the user interface system as a whole).

The Erchonia LunulaLaser™ OTC device user interface includes all points of interaction between the user and the device, including all elements and components of the device and its operation with which the user interacts.

The Erchonia LunulaLaser™ OTC device user interface **components and accessories** are the following:

1. LunulaLaser™ OTC Device
2. Power cord
3. 1 client safety glasses
4. 2 Keys
5. Sani-Cloth Germicidal Wipe (Sample pack)
6. Installation and Proper Use Reference Guide

The device user interface includes the following **controls, visual displays, and visual alarms and alerts**:

1. Touch Screen that displays the:
  - Power Indicator Light
  - Start Screen and related icons, Mode Screen and related icons, including Start, Stop, Pause, and Resume icons and Time Remaining icons.
  - Device Information Screen containing device and manufacturer information.
2. Pull Knobs/Stops
3. Door/Foot Platform
4. Key Switch
5. Diode Light Indicator

6. Magnetic Latch
7. Handle
8. Power Inlet/Fuse Holder

The device user interface includes the following **labeling**:

1. Installation and Proper Use Reference Guide
2. Box Labeling
3. Device Labelling

The device user interface is used by the device user under the following **conditions and sequence of operations**:

1. During initial setup of the device, including opening and unpacking the delivery box components.
2. During establishment of an appropriate device use environment.
3. During preparation and operation of the device, including plugging the electrical cord into the device and an electrical outlet, using the key to power the device on, opening the door/foot platform, using the touchscreen to initiate and manage treatment administration, ensuring correct fitting of the safety glasses to the client, ensuring correct placement of the subject's treatment foot in the device, and using the key to power the device off.
4. Understanding all warnings and precautions contained in the Installation and Proper Use Reference Guide.
5. Cleaning of the device and/or device components and accessories between uses.

The device user interface has been designed such that its use is logical and intuitive such that correct user actions are facilitated and actions that may result in harm (use errors) are prevented or discouraged. Through consideration and initial evaluation of the intended device user characteristics, the intended use of the device and thorough review of design specifications and operational, output, and functional displays of similar devices already on the market with demonstrated safety and efficacy of use by the same intended user population, the logic of information display and control actions have been engineered and designed to be consistent with users' expectations, abilities, likely behaviors and experiences with similar devices at any point during use.

Specifically, the following design elements were considered resulting in the associated logical and intuitive features of the device user interface:

Device User Interface Design Element Considered	Mitigation of Consideration
Device dimensions	
The device design was targeted to be as small, compact, and lightweight as possible, with the following dimensions:
 
 
• Weight: 23lbs / 10.43 kg
 
• Height: 16in/40 cm
 
• Width: 12in/30 cm
 
• Depth: 10in/25.40cm (38 cm with platform extended)
 

The LCD screen (graphic user interface) that provides information to the user.	
The LCD screen displays information pertaining to initiating, pausing, resuming, and stopping treatment; treatment time remaining; and device/manufacturer information.
 
To ensure that readability is always optimal, the LCD screen remains lit throughout the treatment administration process.

Components that the user attaches to the device, i.e., power cord and key.	
Each of these components and the locations on the LunulaLaser™ OTC to which they are attached/inserted have been designed to be intuitive to determine and easy to locate, access and use. The design took into consideration the design of other similar devices currently on the OTC market. Additionally, the Installation and Proper Use Reference Guide has been clearly designed using both text and related labelled images to demonstrate each step of connection, removal, and operation, as applicable, of each individual component to the device, when and as necessary.

Hardware components to control device operation.	
Following correct attachment of all components to the LunulaLaser™ OTC device, the user operates the device using the key and the icons on the touchscreen on the device interface. The key and the touchscreen placement were designed with consideration of intuitive use and ease of use restricted solely to the tasks the user must perform to safely, and effectively, activate and operate the device. The key is easily inserted into the keyhole and turns without effort to power the device on and off. The

	
icons on the touchscreen are activated by gentle touch with the finger and encompass the Start, Stop, Pause, and Resume icons, and the Time Remaining icon.
 
Each icon activation action is verified by the corresponding result being displayed on the touchscreen. This information is also clearly explained using text and images in the Installation and Proper Use Reference Guide.

Safety Glasses	
The LUNULALASER™ OTC is classified by the FDA/IEC as a Class 2 laser device. This represents a current standard for use to ensure the safety of the client. A Class 2 laser is determined to have a chronic viewing hazard. Pointing the laser beam directly into the eye and maintaining it there for an extended period of time could prove to be damaging. To ensure there is no possible instance of residual effect, a pair of specialty safety glasses for use by the client during treatment is provided in the device packaging. The safety glasses, sufficiently and effectively block the laser light spectrum at OD 2+ @ 635nm, OD 0.75 @ 405nm VLT60.
 
Additionally, the following warning is included in the Installation and Proper Use Reference Guide:
 
 WARNING: The client should always be correctly fitted with the safety glasses provided before turning on the laser and doing any treatment.
 
Furthermore, Step 6 of the LunulaLaser™ OTC Treatment Protocol on page 17 of the Installation and Proper Use Reference Guide reads as follows: "Have your client put on the safety glasses..."

Logic of the overall user-system interaction, including how, when, and in what form information (i.e., feedback) is provided to the user.	
Set-up and use of the Erchonia LunulaLaser™ OTC device is designed to be inherently logical and sequential. Information, including visual confirmation via text and lights of user tasks performed are provided in real-time on the LCD and touch screen. These operations and interactions have also been designed with consideration of the design of comparable devices presently on the market.

Packaging and labeling, including the Installation and Proper Use Reference Guide.	Consideration in the design of the packaging and labeling materials was given to ensuring direct compatibility and correspondence between the sequential order of information presented in the Installation and Proper Use Reference Guide and the sequential order of device setup and operation to be performed by the user. All instructional materials contain related text and images for all operations, as applicable. Attention was made to ensuring all potential warnings, cautions and other potential hazards and risks that may potentially occur are included in the Reference Guides, as well as cleaning, troubleshooting, maintenance, and warranty information. As with the other elements of the design and development of the LunulaLaser OTC, consideration was given to the layout and content of Reference Guides/User Manuals for other comparable devices currently on the market.
------------------------------------------------------------------------------------	-------------------------------------------------------------------------------------------------------------------------------------------------------------------------------------------------------------------------------------------------------------------------------------------------------------------------------------------------------------------------------------------------------------------------------------------------------------------------------------------------------------------------------------------------------------------------------------------------------------------------------------------------------------------------------------------------------------------------------------------------------------------------------------------------------------------------------------------------------------------------------------------------------------

#### **6.4. STUDY OBSERVER**

The Study Observer is an Erchonia Corporation employee who is suitably qualified, trained and experienced in conducting Human Factors Validation Testing and is specifically trained to all aspects of the set-up, start-up and use of the Erchonia LunulaLaser™ OTC; and to the information contained in the Installation and Proper Use Reference Guide, and device and package labeling.

The Study Observer's sequential role in this study is to:

- (i) conduct the informed consent process with the user.
- (ii) conduct the study qualification evaluation with the user.
- (iii) observe the user's performance across each of the critical tasks associated with the process of using the LunulaLaser™ OTC from receipt of the packaged device through to operation and use of the device to administer a treatment, and to note his or her observations, including observations of use problems and errors and close calls, throughout the process on the respective Observation Forms.

The Study Observer is trained not to provide any guidance to the user through this process or to answer any questions, simply to observe and to record those observations, unless intervention becomes necessary for safety.

- (iv) conduct a post-test debriefing interview to collect the user's perspectives to supplement the observer's observations, including attaining the user's subjective assessment of any use

difficulties experienced throughout the process of setting up and operating the device; gathering specific feedback on each critical task; and investigating all use difficulties, errors and close calls observed and noted by the Study Observer during the test phase.

- (v) assess the user's understanding of the essential information contained in the Installation and Proper Use Reference Guide, and packaging and device labeling through administration of a knowledge task questionnaire.

## 7. STUDY PROCEDURE

### 7.1. STUDY MATERIALS

The following materials will be employed during this Human Factors Validation Testing.

- (i) Erchonia LunulaLaser™ OTC Installation and Proper Use Reference Guide, contained in **Appendix A**.
- (ii) Box Label for the Erchonia LunulaLaser™ OTC contained in **Appendix C**.
- (iii) User Study Eligibility Evaluation Case Report Forms contained in **Appendix D**.
- (iv) Device Use Study Observer Observation Record Form contained in **Appendix E**.

The Device Use Study Observer Observation Record Form will be used by the Study Observer to record his or her observations pertaining to the user's ability to correctly and safely set-up, start-up and operate the Erchonia LunulaLaser™ OTC.

- (v) Post-Test Debriefing Interview Record Form contained in **Appendix F**.

The Post-Test Debriefing Interview Record Form includes specific assessment of the user's perspectives of the device operation, including attaining the user's subjective assessment of any use difficulties experienced throughout the process of setting up and operating the device; on each critical task; and regarding the specific use difficulties, errors and close calls observed and noted by the Study Observer during the test phase using open-ended and neutrally worded questions.

- (vi) Knowledge Task User Questionnaire contained in **Appendix G**.

The Knowledge Task User Questionnaire includes specific verbal questioning and assessment of the user's understanding of the information contained in the Installation and

Proper Use Reference Guide, and device and packaging labeling using open-ended and neutrally worded questions. This includes assessment of the user's understanding of the indication for use; of how to assemble and operate the Erchonia LunulaLaser™ OTC; of all critical tasks and use scenarios; and of the specific warnings and cautions pertaining to use of the Erchonia LunulaLaser™ OTC.

(vii) Subject User Information and Consent Form contained in **Appendix H**.

## **7.2. STUDY PROCEDURE PROTOCOL**

The following procedure protocol will be implemented sequentially and fully for each enrolled user and treatment recipient, as applicable.

### **7.2.1. SIGNING OF INFORMED CONSENT**

The Study Observer will review the informed consent form with the potential candidate and answer any questions. A candidate who subsequently voluntarily signs the informed consent form will be enrolled as a user in the study and receive a unique de-identified subject ID. The Subject ID will comprise the Study Observer's first and last name initials followed by a 2-digit number from 01 onwards determined by the user's order of sequential enrollment. For example, the fifth user to be enrolled in this study will have a unique de-identified subject ID of TS05.

### **7.2.2. ELIGIBILITY EVALUATION**

#### **7.2.2.1. User**

The Study Observer conducts the user eligibility evaluation to confirm that the user fully qualifies to take part in the study.

### **7.2.3. PROVISION OF STUDY DEVICE**

The user is provided with the Erchonia LunulaLaser™ OTC in its intended packaging that also contains the Installation and Proper Use Reference Guide exactly as is intended to be supplied following FDA market clearance. The user is instructed to open the packaging and prepare the device for use exactly as they would if they were to receive it at their place of employment.

**N.B.:** There will be no participant training in preparation or use of the device in this Human Factors Validation Testing study as it is not intended that users receive any training once the device has market clearance. It is intended that the user will receive delivery of the device in its packaging at

the place of employment. The user will need to set-up and operate the device based upon the information provided with the packaging, and therefore, this Human Factors Validation Testing study will also not implement user training to optimally simulate intended use of the Erchonia LunulaLaser™ OTC in real life. Additionally, users will be left to work out how to operate the Erchonia LunulaLaser™ OTC and to administer a treatment as independently and naturally as possible, without interference, influence, or instruction from the Study Observer, including whether or not the user chooses to read the instructional materials provided including the Installation and Proper Use Reference Guide.

#### **7.2.4. USER USE OF DEVICE**

The user is instructed to operate and use the device to administer treatment to the client following the exact process he or she would follow as if the device had just been received via delivery at his or her place of employment.

As this process is ongoing, the Study Observer will observe the user's performance from opening of the packaged device through to operation and use of the device, or otherwise to as far as the subject is able to complete the process, and will note his or her observations, including observations of use difficulties/problems, errors, and close calls on the Device Use Study Observer Observation Record Form (**Appendix E**).

The Study Observer will not provide any verbal, written or any other form of guidance or assistance to the user throughout this process, and although the Study Observer will record any questions asked by the user during this process, he or she will not answer any questions the user may ask or otherwise interfere in the process, unless intervention becomes necessary for safety reasons.

#### **7.2.5. POST-TEST DEBRIEFING INTERVIEW**

Once the user indicates that he or she has completed the device use and treatment application process, the Study Observer will conduct the Post-Test Debriefing Interview (**Appendix F**). The Study Observer will record verbatim the user's responses to each question but will otherwise not react to the user's responses. The Study Observer will not explain or reword any of the questions in the Knowledge Task Patient User Questionnaire and will not provide any guidance or feedback regarding the user's responses in any manner.

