### **7.2.6. KNOWLEDGE TASKS EVALUATION**

The knowledge tasks evaluation will take place once the Post-Test Debriefing Interview is complete. The knowledge tasks evaluation commences with the Study Observer requesting that the user read through the Installation and Proper Use Reference Guide and all other labeling information contained on the device and the packaging regardless of whether or not he or she did so during the use evaluation study component. The Study Observer will not point out any specific information in any of these materials to be read or noted, and although the Study Observer will record any questions asked by the user during the material review process, he or she will not answer any questions the user may ask or otherwise interfere with the process in any manner.

Once the user indicates that he or she has completed reading the supplied materials, the Study Observer will administer the Knowledge Task Patient User Questionnaire (**Appendix G**). The Study Observer will record verbatim the user's responses to each question but will otherwise not react to the user's responses. The Study Observer will not explain or reword any of the pre-established questions in the Knowledge Task Patient User Questionnaire and will not provide any guidance or feedback regarding the user's responses in any manner.

Following completion of the knowledge tasks evaluation, the user's participation in the study is complete.

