### **11.2.1. Root Cause Analysis**

Observational and knowledge task data will be aggregated with the debriefing interview data and analyzed in detail to determine the root cause of any identified and/or reported use difficulties and/or errors, including close calls. The analysis will include evaluation of how the use errors or problems occurred within the context of device use, including the specific aspect of the user interface that caused problems for the user.

The root causes of all use errors and problems will be considered with respect to the associated risks to ascertain the potential for resulting harm and to consequently determine the need for and priority of implementing additional risk management measures.

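### Section 7.2.5 carries the knowledge questionnaire's conduct rules into the debriefing, names the wrong instrument, and leaves it in doubt whether the observer may probe an answer

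*Combined protocol and SAP*

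**What the plan says.** Section 7.2.5 has the Study Observer conduct the debriefing with Appendix F once the user reports having finished. Three conduct rules follow:

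- On answers: "The Study Observer will record verbatim the user's responses to each question but will otherwise not react to the user's responses".
- On questions: the observer "will not explain or reword any of the questions in the Knowledge Task Patient User Questionnaire".
- On feedback: the observer "will not provide any guidance or feedback regarding the user's responses in any manner".

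Section 7.2.6 then describes the knowledge task, which starts only when the debriefing is complete. It ties the questionnaire named above to Appendix G and gives the same rules, with the observer told that he or she "will not explain or reword any of the pre-established questions in the Knowledge Task Patient User Questionnaire".

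Two other sections describe what the debriefing is for. Section 6.4(iv) gives the observer the task of "investigating all use difficulties, errors and close calls observed and noted by the Study Observer during the test phase". Section 7.1(v) says the Appendix F form asks for the user's view of, among other things, "errors and close calls observed and noted by the Study Observer during the test phase using open-ended and neutrally worded questions".

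Section 11.2.1 states the use made of the answers: "Observational and knowledge task data will be aggregated with the debriefing interview data and analyzed in detail to determine the root cause". That analysis is to show how each problem arose, "including the specific aspect of the user interface that caused problems for the user".

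**The concern.** A knowledge test and a debriefing need different interviewer behaviour. In a knowledge test, a reaction or a reworded question can give the answer away, so silence protects the measurement. In a debriefing about cause, the first answer is often incomplete. A user may say that the screen was confusing without saying which screen, what was expected of it, or what he or she was trying to do. A neutral follow-up question is then the way to learn more.

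Section 7.2.5 gives the debriefing the rules of the test. Section 8.1.2 commits the observer to perform the study according to the protocol, so a careful observer could take 7.2.5 as an instruction not to follow up an unclear answer. The cause of that event would then have to be inferred by the analyst. Under 11.2.2, the findings on cause lead to changes in the interface and labelling, so a poorly documented cause can lead to the wrong change or to none.

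**Working it through.** No arithmetic applies. The check compares the sections and asks what each sentence does to the debriefing.

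**Step 1: compare the rules of 7.2.5 and 7.2.6.** The sentence on recording and not reacting is the same in both. The sentence on rewording, guidance and feedback differs by one word: 7.2.6 describes the questions as pre-established and 7.2.5 does not. Both name the knowledge questionnaire. In 7.2.5 that instrument is not in use, because 7.2.6 places it after the debriefing. Either the sentence was carried over by mistake, or it was meant for Appendix F and names the wrong form. Both readings call for a correction.

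**Step 2: ask what each rule does to the debriefing, read literally.**

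| Rule in 7.2.5 | Object it names | Effect on debriefing questions |
|---|---|---|
| No reaction to answers | The user's responses in the debriefing | Excludes a probe prompted by an answer |
| No explaining or rewording | The knowledge questionnaire (Appendix G) | None by its own words |
| No guidance or feedback | The user's responses | Excludes correction and teaching, but not a neutral question |

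Only the first rule restricts follow-up.

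**Step 3: set that rule against 6.4(iv) and 7.1(v).** These sections provide for questions triggered by an event: the observer notes an error and asks about it in open-ended terms. They do not say whether a second question may follow from the reply. Section 6.4(iv) speaks of investigating, which ordinarily includes pursuing an unclear reply, while 7.2.5 says not to react to it. The conflict is confined to questions triggered by an answer.

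**Step 4: ask whether the other two data sources fill the gap.** Section 11.2.1 combines three sources.

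- Observation records what the user did. It does not directly show what the user perceived or intended.
- The knowledge task is given after every user has been asked to read the Guide and labelling, whether or not he or she did so during use (7.2.6). Its answers may therefore not reflect what the user understood when the error occurred.
- The debriefing comes before that reading, and is the only one of the three that asks users for their own account of the specific events in their session.

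The other sources contribute, but neither replaces the user's account. This matters most for the unanticipated errors that 5.5.2 allows for, since questions written in advance are least likely to fit them.

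**Step 5: ask whether a missed probe can be recovered.** Participation ends with the knowledge task (7.2.6). Record forms carry no identifying information (8.1.1), and no later contact with users is planned. Retesting under 11.2.3 is optional and concerns the modified interface. The plan therefore has no step at which an unclear debriefing answer would be clarified.

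**Step 6: consider the size.** The documents give no expected number of errors and no share of answers that would need a probe. At the low end nothing is lost, if Appendix F scripts the probes and observers use them, or if first answers suffice. At the high end the loss covers every recorded difficulty, error and close call whose first answer does not identify a cause.

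**The case against.** The strongest reply is that 7.2.5 contains a copying slip and nothing more. The no-rewording clause is limited to the knowledge questionnaire and so restricts nothing in the debriefing. Not reacting and giving no feedback can be read as ordinary interviewer neutrality, and a neutral question is neither. Sections 6.4(iv) and 7.1(v) already plan open-ended questions on each observed event, and nothing limits the debriefing to a fixed list. Root cause analysis has two further sources, and Appendix F may already contain suitable probes.

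Much of this stands. A reader might infer from 7.2.5 that follow-up questions are barred altogether, or that root cause analysis cannot be done. The documents do not support either inference. The observer can ask about each specific event and make clear which event is meant, and the analysis does not rest on the debriefing alone. Nor do the documents call the debriefing the main source on cause; its particular value is an inference from its timing and content.

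What does not fall away is the no-reaction sentence. It applies to debriefing answers in terms, and it can be read either as neutrality or as a prohibition on probing. Observers who read it differently would collect different data. If Appendix F does script probes, 7.2.5 should still make clear that they may be used.

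**Conclusion.** The point holds as an internal inconsistency with a limited practical consequence. Section 7.2.5 names the wrong instrument, which is certain from the text. Its no-reaction sentence, followed literally, excludes neutral probes prompted by an answer and so conflicts with the duty in 6.4(iv) to investigate each observed problem. The effect would be poorer information on cause for 11.2.1, in an unknown number of events, with no planned way to recover it.

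This rests on two assumptions: that an observer would follow 7.2.5 as written, and that Appendix F, whose content was not available, does not already provide for probes. It should be corrected before testing begins. It does not invalidate the design.

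**What to change.** In 7.2.5, delete the reference to the Knowledge Task Patient User Questionnaire and replace the no-reaction sentence with wording such as:

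> After the Appendix F questions, the observer may use neutral, non-leading probes about each recorded difficulty, error and close call, for example what the user saw, expected or was trying to do. The observer accepts a reply that the user does not know, writes replies down word for word, and gives no correction or teaching.

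Accepting such a reply guards against pressing users to supply a cause. Excluding correction and teaching protects the knowledge task that follows. Keep the no-rewording and no-reaction rules in 7.2.6 only. If Appendix F already lists probes, refer to them in 7.2.5.

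The cost is one paragraph, with a short list of example probes, and a few more minutes per interview with the same observer. No change to the sample, the device session or the analysis is needed.
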